5.4.2 Secondary efficacy variables

5.4.2.1 Change from baseline to Week 108 in fatigue-related symptoms as measured by the FSIQ-RMS symptoms score

The Fatigue Symptom and Impact Questionnaire-Relapsing Multiple Sclerosis (FSIQ-RMS) is a validated patient reported outcome instrument from which a fatigue symptoms score and sub-domain impact scores can be obtained, where higher scores indicate greater fatigue or impact [Protocol appendix 9]. The questionnaire consists of 2 parts: section 1 is a daily diary and is answered during 7 consecutive days. Section 2 is a weekly diary and is answered on the 7th day of the 7 consecutive days where the daily diaries were filled in. The questionnaire is completed using an electronic device that automatically tracks the completion date. Data are transferred electronically to the sponsor.

FSIQ-RMS is completed during the pre-randomization period (i.e., at Visit 2: 7 consecutive days preceding the randomization [Baseline visit]), and during the post-randomization period, i.e., at scheduled Visits 6, 7, 10, and 12 (Weeks 12, 24, 60, 84, respectively), 14 (Week 108), as well at premature EOT visit and at unscheduled visits (due to relapses or other unscheduled visits). If applicable, it is also completed at the corresponding visits in the PTO. For more details refer to [Table 2–Table 4](#).

FSIQ-RMS **symptoms domain (FSIQ-RMS-S)** consists of 7-items assessing fatigue related symptoms collected as a daily diary (section 1) on an 11-point numeric rating scale (0–10) with a 24-hour recall period.

The **FSIQ-RMS-S score** may be computed as a daily or weekly 0 to 100 score (higher score implies greater fatigue). To be able to compute a daily symptoms score, at least 4 items of the symptoms diary must be non-missing; otherwise the score is considered “missing”. For each 7-day weekly score, at least 4 reported diaries with at least 4 items completed on each diary day are needed to calculate the FSIQ-RMS-S weekly score. If fewer than 4 diaries with data on at least 4 items are available within the 7-day period, then the weekly score is considered as “missing”. Details of the scoring rules to calculate FSIQ-RMS-S daily and weekly scores as well as rules to define baseline and post baseline FSIQ-RMS-S weekly scores are given in the Appendix [C.2](#).

Change from baseline in FSIQ-RMS symptoms score is defined as the absolute change from baseline to each time point.

5.4.2.1.1 Variables for supplementary analysis

For supplementary analyses change from baseline for the following weekly scores will be considered in addition separately:

- **Up to EOT + 7 days**
- **Per protocol** - for subjects in the PPS data up to the first protocol deviation leading to exclusion from the per protocol analysis

- **LOCF by visit** weekly scores by visit based on last observation carried forward (LOCF) will be derived. Baseline data will not be carried forward.

5.4.2.2 Cumulative number of combined unique active lesions (CUAL) from baseline to Week 108

CUAL from baseline to Week 108 is calculated as the sum of new T1 Gadolinium-enhanced (Gd+) lesions and new or enlarging T2 lesions without Gd enhancement on T1 at all post-baseline MRI visits up to the Week 108 MRI visit (if the Week 108 visit is missing, consider all post-baseline scans up to EOS).

MRI scans are scheduled at Baseline, at the Week 60 Visit, and the Week 108 Visit. For subjects who prematurely discontinue treatment, an additional premature EOT visit MRI is scheduled. Unscheduled MRI scans may be conducted in addition.

MRI data are read centrally and provided to the sponsor.

To account for varying observation time, e.g. in case of premature study withdrawal or missing MRI assessments, the analysis will be adjusted by: $\text{Time up to the last MRI (years)} = (\text{Date of last MRI considered in derivation of CUAL} - \text{Randomization date} + 1) / 365.25 \text{ days}$.

Rationale: Due to the fact that yearly MRI scans are scheduled, the CUAL count is expected to be mainly driven by new T2 lesions. The number of T2 lesions is expected to increase with observation time. In contrast, in studies where MRI scans are scheduled more regularly, the CUAL count is mainly driven by new T1 Gd+ lesions which are expected to increase with the ‘Number of MRI scans’ conducted. Also, in this study, there is an additional MRI following premature treatment discontinuation which can occur at any time, therefore the ‘number of MRI scans’ is not necessarily expected to be a good approximation of the observation time.

5.4.2.2.1 Derivations details

The central reader provides the ‘Number of new T1 Gd+ enhancing lesions’ (variable T1GdNew_R) and ‘Number of new T2 lesions without Gd enhancement’ (variable T2New_R) at a visit as compared to the last scheduled MRI scan (with premature EOT visit being considered a scheduled MRI). At the first scheduled post-baseline visit comparison is made to baseline (with baseline defined as the Baseline Visit 2, or Visit 2 - 2nd attempt if available [see Section 5.4.3] for details and a rationale).

CUAL from baseline to Week 108 is derived as the sum of ‘Number of new T1 Gd+ enhancing lesions’ and ‘Number of new T2 lesions without Gd enhancement on T1’ across all post-baseline MRI visits up to the Week 108 MRI visit (if missing up to EOS) irrespectively if a visit is conducted during PTOP or not.

For subjects without unscheduled MRI visits this includes MRIs from the Week 60 Visit, Week 108 Visit, and if applicable premature EOT visit.

As only the number of new lesions as compared to the last scheduled visit is recorded by the central reader, lesions are not expected to be double counted when summing over scheduled visits.

In the rare event that the Baseline MRI visit is conducted after randomization date, the variable is derived in the same way, i.e., based on the nominal visit. Note that effectively the derived variable then covers a period starting slightly after randomization. If the baseline MRI is missing, new or enlarging T2 lesions as compared to baseline cannot be assessed and consequently the endpoint is considered missing. The baseline MRI is considered missing if presence of T1 Gd+ lesions at baseline is missing.

For subjects with at least one unscheduled post-baseline MRI scan, care needs to be taken in the derivation to avoid double counting of lesions and the following algorithm applies:

- If a subject has an unscheduled MRI which is the last available MRI in the time period considered (i.e., if Week 108 MRI visit is missing, last MRI result up to EOS): Include that last unscheduled MRI when deriving CUAL in the same way as for scheduled visits.
- If a subject has an unscheduled MRI which is not the last available MRI for the subject: Do not include that unscheduled MRI. Rationale: New / enlarging lesions at the unscheduled MRI as well as at the later scheduled MRI are reported in reference to the previous scheduled visit. Including both may result in double counting.

5.4.2.2.2 *Variables for supplementary Analysis*

CUAL up to EOT + 7 days

Defined as the cumulative number of combined unique active lesions from baseline to EOT + 7 days. Includes only MRI scans conducted after randomization and prior to EOT + 7 days (last drug intake + 7 days). All other derivations follow the same approach as for CUAL from baseline to Week 108, in Section 5.4.2.2. Note that unscheduled MRI assessments previously not included may now be included in the derivation, if they become the last MRI assessment in the newly considered period. The time up to the last MRI scan used in the derivation is calculated.

Subjects completing treatment with complete MRI information will be flagged (completing treatment, with baseline MRI scan available, and all post-baseline scheduled MRI scan results [Week 60 and Week 108] available and conducted up to EOT + 7 days). This will allow for a complete-case analysis, if needed.

CUAL up to EOS or per protocol exclusion

Defined for subjects in the PPS as the cumulative number of combined unique active lesions from baseline to first deviation leading to exclusion from the per protocol analysis. Includes only MRI scans conducted after randomization and prior to per protocol exclusion date. All other derivations follow the same approach as for CUAL

from baseline to Week 108, in Section 5.4.2.2. The time up to the last MRI scan used in the derivation is calculated.

5.4.2.3 Time to 12-week Confirmed Disability Accumulation (CDA) up to EOS

5.4.2.3.1 Main analysis of secondary endpoint

Time to first 12-week CDA is defined as the time from start date of the first onset of 12-week CDA minus date of randomization + 1 in days. Subjects without 12-week CDA are censored, following the rules below. It is assessed from baseline up to EOS.

Assessing disability by EDSS

Disability as measured by EDSS is assessed in all subjects at screening, baseline, and thereafter at scheduled visits every 12 weeks until the end of study. Additional EDSS assessments for individual patients may be conducted between scheduled visits (i.e., during an MS relapse). The EDSS is a disability scale that ranges from 0 (normal) to 10.0 (death) in 0.5-point steps (1-point step from 0 to 1). It is based on standard neurological examination in conjunction with observations concerning ambulation. For analysis the overall EDSS score as reported by the investigator from the eCRF is considered (Field: 'Expanded disability status scale').

EDSS increase criteria for disability accumulation

The following criteria for an increase in EDSS in derivation of disability accumulation apply:

- Increase of at least 1.5 in EDSS for subjects with a baseline EDSS score of 0;
- Increase of at least 1.0 in EDSS for subjects with a baseline EDSS score of 1.0 to 5.0;
- Increase of at least 0.5 in EDSS for subjects with a baseline EDSS score ≥ 5.5 ;

where baseline EDSS is defined as the last available EDSS score prior to or on the date of randomization.

12-week CDA

A 12-week CDA is an increase in EDSS as compared to baseline according to the criteria above which is confirmed at a scheduled visit after 12 weeks. The increase needs to be persistent at all EDSS assessments (scheduled or unscheduled) between onset (first EDSS increase in the considered period) and confirmation. 12-week CDA is assessed sequentially up to the last available EDSS assessment for a subject in the study following the algorithm detailed below.

Disability progression can only be confirmed at a scheduled visit, where the EOT (Visit Week 108 or premature EOT visit), and FU visits count as scheduled visits, outside of an ongoing relapse. In this context, relapse duration is defined as period between start date (inclusive) and end date (exclusive) if available and limited to 90 days from onset if end date is not available or duration is longer than 90 days.

Algorithm for deriving 12-week CDA

1. For all post-baseline EDSS assessments (scheduled or unscheduled) assess if the absolute change from baseline meets the EDSS increase criteria for disability accumulation, described above. Start with the first EDSS assessment that meets the criteria for EDSS increase. Onset date of the corresponding potential 12-week CDA is the EDSS assessment date.

2. Confirmation of EDSS increase:

a. An EDSS increase of a potential 12-week CDA has to be confirmed by an EDSS increase at a scheduled visit, at least 70 days*, from the onset date of the potential 12-week CDA.

* Note: As visits are scheduled every 12 weeks with a time window of ± 7 days for conducting the EDSS assessment, the minimum per-protocol allowed time difference between two EDSS assessments scheduled 12 weeks apart is 70 days (12 weeks = 84 days minus a 7-day visit time window for each of the 2 visits, i.e., 84 days – 14 days = 70 days).

EDSS assessments conducted during a relapse, i.e., from relapse start date (inclusive) to minimum of relapse end date and relapse start date + 90 days (exclusive) are not considered for confirmation.

If an EDSS increase cannot be confirmed due to no available EDSS assessment, but the subjects dies due to MS (experiences a relapse with outcome death, or death with reason ‘Multiple sclerosis’) the CDA is also considered confirmed, with confirmation date being the death date and onset date the initial EDSS increase.

b. A confirmed EDSS increase as per (a) is considered persistent if every EDSS score available (scheduled or unscheduled) between the onset and the confirmation date of a potential 12-week CDA meets the EDSS increase criteria. The initial EDSS increase is considered a 12-week CDA.

If any EDSS from onset to confirmation does not meet the EDSS increase criteria, the increase is not persistent and the initial EDSS increase is not considered a 12-week CDA.

3. Repeat step 2 for all EDSS assessments with an EDSS increase as per the criteria above for disability accumulation, starting with the first possible onset, by date, up to the last possible onset. Once a 12-week CDA is identified the algorithm can stop.

4. If at none of the assessments a 12-week CDA is identified, but the subject dies due to MS (experiences a relapse with outcome death) the subject is considered to have a 12-week CDA with onset date being the death date.

5. If no 12-week CDA is identified, the subject is considered censored with the censoring date derived according to the rules below.

Censoring

Censoring date is defined as: Date of last EDSS assessment without an EDSS increase. Time to censoring is defined as censoring date minus date of randomization + 1.

Subjects without post-baseline assessment are censored on randomization date. Similar, subjects without CDA who have only EDSS assessments with an EDSS increase that cannot be confirmed, are censored on randomization date. For subjects without baseline EDSS score, missing values are assigned.

Handling of missing dates

Missing dates for EDSS assessments will be imputed as follows:

- Partial date: Maximum of 'lower limit', 'previous scheduled EDSS assessment according to the visit label' + 1 day (if available), and 'randomization date'
- Missing date: do not impute and exclude from analysis

Missing dates for relapse start and end dates will be handled as follows:

- Partial or missing relapse end date with available relapse start date: use relapse start date + 90 days or upper limit of partial end date if earlier.
- Partial relapse start date: If only day is missing, consider the relapse has started on the last day of the month (or on relapse end date – 1 day if earlier) and ended 60 days later or at (upper limit of a partial) relapse end date, if earlier. If the month or year are missing the relapse does not lead to non-consideration of an EDSS assessment.
- Missing relapse start date: Corresponding relapse does not lead to non-consideration of an EDSS assessment. Do not consider imputed relapse start dates.

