5.4.1.1 General derivation details for relapses

A relapse (confirmed or unconfirmed) is identified from the ‘Relapse Summary’ eCRF with ‘Did the subject experience a relapse’ ticked as ‘Yes’. For each relapse the corresponding start and end date/time, as well as outcome, treatment with corticosteroids, action taken with study drug and need for hospitalization, and whether an EDSS was completed are recorded. For relapses with completed EDSS it is collected whether it qualifies as a confirmed relapse (see definition details for primary efficacy variable above). A relapse which is not a confirmed relapse is considered an ‘unconfirmed relapse’.

Relapses ‘from date of randomization up to EOS date’ include all relapses unless starting prior to randomization. Additional flags will be added for relapses from date of randomization up to EOT + 7 days (relapse start date in respective period), relapses after EOT + 7 days (start date from EOT + 8 days).

Note: Relapses with missing start date are considered to have started on randomization date for analysis. Relapses with partial start date are considered to have started at the lower limit (but earliest on randomization date).

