5.4.2.4 Time to 24-week CDA

5.4.2.4.1 Main analysis of secondary endpoint

The derivation of the variables for Time to 24-week CDA up to EOS follows the same approach as described in Section 5.4.2.3.1, but onset of progression is to be confirmed after 24 weeks (≥ 154 days, i.e., 168 days – two times 7-day visit time window) instead of after 12 weeks. The progression has to be persistent between onset and confirmation.

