5.5.3 Deaths

Death information (date of death and primary cause) is taken from the Death eCRF.

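### The CDA algorithm defines death due to MS more narrowly in step 4 than in step 2a, so an MS-attributed death without a fatal relapse is an event or a censoring depending on whether an EDSS rise was still open at death

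*SAP*

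**What the plan says.** SAP 5.4.2.3.1 derives 12-week CDA in five steps, and death due to MS enters twice.

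- **Step 2a** covers a rise that is still open. Its condition is "If an EDSS increase cannot be confirmed due to no available EDSS assessment". If the subject then dies due to MS, the rise counts as confirmed, with onset at the rise. The bracket explaining that phrase reads "experiences a relapse with outcome death, or death with reason", followed by the category 'Multiple sclerosis'.
- **Step 4** covers subjects for whom no assessment led to a CDA: "but the subject dies due to MS (experiences a relapse with outcome death) the subject is considered to have a 12-week CDA", with onset on the death date.
- **Step 5** deals with everyone left: "If no 12-week CDA is identified, the subject is considered censored". The censoring date is "Date of last EDSS assessment without an EDSS increase".

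The two criteria come from different forms. Section 5.4.1.1 takes relapse outcome from the Relapse Summary form: "For each relapse the corresponding start and end date/time, as well as outcome". Section 5.5.3 takes the cause of death from elsewhere: "Death information (date of death and primary cause) is taken from the Death eCRF".

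Section 5.4.2.4.1 carries the algorithm over to 24-week CDA, which "follows the same approach as described in Section 5.4.2.3.1, but onset of progression is to be confirmed after 24 weeks".

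**The concern.** One algorithm explains the same phrase in two ways, and the second explanation drops a criterion that the first includes. Because the criteria rest on separate forms, a death can be attributed to MS on the Death form with no relapse recorded as fatal. Such a death is an event in one branch and a censoring in the other.

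Time to 12-week CDA and time to 24-week CDA are both tested within the multiplicity strategy of section 9.1.1, so their event definitions should be settled before unblinding. The EDSS itself places death at its top score of 10, so censoring an MS death at an earlier assessment without an increase fits poorly with what the endpoint measures.

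**Working it through.** The SAP gives no figure to reproduce here. The check applies steps 2a, 4 and 5 to each combination of type of MS death and EDSS history. An open rise means an EDSS increase still unconfirmed at death because no later EDSS was available. No open rise means either no increase at all or an earlier increase that failed the persistence requirement in step 2b. The table is for subjects with no CDA already confirmed.

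| Case | Type of MS death | Open rise? | Deciding step | Result |
|---|---|---|---|---|
| 1 | Fatal relapse | Yes | 2a | Event, onset at the rise |
| 2 | Fatal relapse | No | 4 | Event, onset at death |
| 3 | Reason 'Multiple sclerosis', no fatal relapse | Yes | 2a | Event, onset at the rise |
| 4 | Reason 'Multiple sclerosis', no fatal relapse | No | 4 not met, then 5 | Censored at the last EDSS without an increase |

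Cases 1 and 2 show that the plan does not reserve MS death for subjects with an open rise: a fatal relapse counts either way. Cases 3 and 4 are the same kind of death with opposite event status.

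**Effect of aligning the definitions.** If step 4 takes the step 2a definition, case 4 changes from censored to an event on the death date. If step 2a takes the step 4 definition, case 3 changes from an event to censored. Either removes the mismatch, and each affected subject moves the event count by one.

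**Which analyses can change under the first option.**

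- *12-week and 24-week main analyses:* both use these steps. A subject with a confirmed 12-week CDA that later reversed already has the 12-week event, so only the 24-week result could change.
- *EOT + 7 versions (5.4.2.3.2.2 and 5.4.2.4.2.2):* onset must fall no later than EOT + 7 days. Step 4 onset is the death date, so a later death changes nothing.
- *Per-protocol versions (5.4.2.3.2.1 and 5.4.2.4.2.1):* MS deaths count only up to the per-protocol exclusion date, which after premature treatment discontinuation is EOT + 7 days (7.1.3). These sections refer to deaths due to MS without defining the term, so they do not resolve the difference.

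**Search for a reconciling definition.** No other section gives a common definition of death due to MS or a reason for the narrower step 4 wording. Section 5.4.2.3.1 describes EDSS 10 as death, but the analysis uses the score the investigator reported, and nothing says that deaths are entered as EDSS 10. If they were, the entry would be a rise and step 2a would apply.

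**The case against.** The strongest defence is that the difference could be deliberate. In step 2a a measured EDSS rise exists and the death only confirms it; in step 4 the death alone creates the event, and stricter evidence would be defensible there. This stands as a possibility, but the SAP does not state it, and using one phrase for both steps points the other way. Another reading is that the step 4 bracket is shorthand for the step 2a definition. The slip is then editorial and no death is lost, but the text still needs correcting because a programmer following the bracket would censor.

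A reader might infer more than the text supports:

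- *That any earlier EDSS rise decides the outcome.* It does not. A non-persistent earlier rise also leads to step 4 and then to censoring.
- *That every death with reason 'Multiple sclerosis' and no open rise is censored.* A death that is also a fatal relapse meets step 4 and is an event.
- *That every version of the endpoint changes.* The per-protocol and EOT + 7 windows limit this, as shown above.
- *That the plan leaves event status open to choice.* Read literally, each case has exactly one outcome. Room for choice arises only if step 4 is taken as shorthand.

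The combination needed is also unusual. The deviation code list treats age over 55 at screening, and EDSS above 5.5 at screening or baseline, as deviations, and planned treatment lasts 108 weeks.

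**Conclusion.** The inconsistency is real on the plain text. It is confined to deaths attributed to MS with no fatal relapse and no EDSS rise open at death, which steps 4 and 5 censor while step 2a would count the same kind of death as an event. The SAP gives no expected number of MS deaths, so no effect on either CDA test can be calculated; zero to very few subjects is an assumption, and a material effect on the tests is not shown. The point is minor, but worth settling because it concerns the event definition of two confirmatory secondary endpoints.

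**What to change.** Define death due to MS once in section 5.4.2.3.1, in the step 2a sense: a relapse ending in death, or a death whose recorded reason is 'Multiple sclerosis'. Refer to that definition in steps 2a and 4 and in the per-protocol variants in 5.4.2.3.2.1 and 5.4.2.4.2.1. The 24-week endpoint then inherits it through 5.4.2.4.1. If the narrower step 4 rule is intended, say so and give the reason before unblinding.

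The cost is one phrase and its cross-references, plus a check that the derivation program matches. Both forms are already collected, so no new data are needed.
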